**11. Benefits.**

Describe any potential direct benefit(s) to subjects in this study, if any and the importance of the knowledge that may reasonably be expected to result. Within the description, do not include payment to subjects as a benefit.

The proposed research is designed to evaluate the value-added benefit of embedding WTM caregiver training within a more comprehensive MISC ECD program so as to better prevent the toxic effects of cassava on the developing brain in very young children. Also, we hope to identify key biomarkers of early childhood neurodevelopment that can be utilized to monitor the health risks associated with the consumption of poorly processed cassava. Finally, for the present mothers in konzo-affected communities in the DRC, we hope to see whether MISC can provide the same mental health benefits and the caregiving functionality in activities of daily living, and diminished depression and anxiety mental health benefits as evidenced in its application with Ugandan mothers with HIV. Throughout the recruitment process and the course of the study, villagers will learn that they need to correctly process cassava prior to its consumption and also, diversify their diet. This type of information is already given to the population by the PRONAUT team and will be just emphasized during interviews with villagers. The long-term benefit for healthy subjects is a reduced risk for konzo. For individuals at risk for konzo (mothers and even very young children; [name] et al., 2017), the long-term benefit is a reduced risk for advancement of spastic paraparesis and associated neurodevelopmental disability. Reduced exposure of pregnant women and children to cyanogens should also promote brain development by reducing the risk for thiocyanate-induced hypothyroidism and/or cyanate-induced neurotoxicity.

Prevention of the risk of spastic paraparesis (konzo) in children and adults reduces chances of lifelong disability and societal stigma. This greatly outweighs the minimal risk of bruising or infection following phlebotomy. Automated eye tracking data will be gathered for two of the neurodevelopmental assessments (Fagan Test of Infant Intelligence working memory for human faces; Early Childhood Vigilance Test of attention). These data can be explored and evaluated for what they can provide in terms of additional neuro-ophthalmological and eye motility indicators of pre-clinical or early onset konzo disease in very young children. This has not been done before with pediatric konzo disease, and is a highly innovative feature of the present study proposal.

## 12. Screening, Recruitment, and Determining Eligibility.

### A. Describe the criteria for who will be included or excluded from the study, including how subjects will be screened for eligibility

The proposed study will enroll 100 households from villages not presently enrolled in the R01 study. Eligible households must have at least one child less than 4 years of age, and the biological mother of the child must be the primary caregiver and food provider for the child. Eligible households may NOT have an older child or other family member already affected by konzo, thus the results will be generalizable to a broader population. Enrollment and randomization will occur at the village level. After 100 households with children 1-4 years of age complete baseline assessments, 66 of them will be randomly selected to undergo individualized MISC+WTM training sessions by peers trained in the MISC+WTM curriculum, who will come to their homes for a 1 to 2 hr. session on a biweekly basis.

**Exclusion Criteria.** At pre- study medical examination we will exclude children with a medical history of serious birth complications, severe malnutrition, bacterial meningitis, encephalitis, cerebral malaria, or other known brain injury or disorder requiring hospitalization. Also children with seizure or other neurological disability will be excluded. Serious CNS neurodisabilities would prevent such children from completing the MISC intervention, and possibly significant portions of the neuropsychological test battery.

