**1. Hypothesis / Objective / Goals / Aims.**

Briefly describe the study's hypothesis / objectives / goals / aims.

Konzo is a neurological disease associated with chronic reliance on poorly processed cyanogenic cassava as the main source of food. We found that school age children from konzo areas present with poor neurocognition compared to those from nearby non-konzo areas, persisting and worsening even 4 years after initial assessment. Our most recent work has extended these findings to children as young as a year in age, suggesting that the neurodevelopmental impact from cassava cyanide neurotoxicity may begin as soon as children are weaned from breast milk to cassava porridge. The “wetting method (WTM)” is a simple and effective method of detoxifying cassava flour prior to eating that is being taught to rural women in a clinical-trial study by our group in the Democratic Republic of Congo (DRC). The present proposal seeks to combine a curriculum of mediational intervention for sensitizing caregivers (MISC) with a WTM training program (MISC/WTM). MISC is an early childhood development (ECD) caregiver training program previously demonstrated in clinical trials by [name] and colleagues to improve health, neurodevelopmental, and caregiver mental health outcomes in rural Ugandan HIV-affected households. Training 66 randomly selected moms from a cohort of 100 on MISC/WTM (while the remaining 34 get WTM only) will better sensitize mothers to their children’s development, leading to better WTM adherence while providing practical ECD benefits.

The Aims for this study are:

1. To establish the feasibility of adding a biweekly 1-year MISC/WTM training program for mothers and their 1 through 4-year-old children, led by peer trainers from the community. MISC has been previously implemented for HIV-affected households in Uganda, but not for konzo communities in the DRC.

2. To document whether better adherence to WTM through MISC will lead to lower household flour cassava cyanogenic content and lower urinary thiocyanate (U-SCN) levels in the mother/child dyads. We will also test for improved child outcomes on the Fagan Test of Infant Intelligence (with automated eye tracking), Mullen Scales of Learning (MSEL), the Early Childhood Test of attention (ECVT; eye tracking), and the Color-Object Association Test (COAT). Caregiver depression/anxiety and corresponding functionality for activities of daily caregiving should also significantly improve.

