on project timeline and resources. With n=66 in MISC+WTM arm and n=34 in WTM only arm. Based on our clinical studies with a biweekly MISC caregiver training with mothers with HIV in rural eastern Uganda, we expect an over 90% retention rate for the full year. With this retention rate, the unadjusted effect size of 0.60 is detectable as statistically significant with power of 0.80 and 0.05 level of significance in two-tailed tests, that is differences between trial arms of 0.6 of the standard deviation or greater will be captured with statistical significance. For the main trial arm effect (differences between arms over time) from two repeated measures at 6 and 12 months with the planned covariance adjustment for baseline, the adjusted standard deviation is smaller than the unadjusted due to the reduction in error variance. Assuming correlation of 0.4 between pairs of repeated measures seen in past testing of MISC, the adjusted detectable effect size is 0.44. This effect size is consistent with past testing of MISC in HIV-affected households that produced effect sizes ranging from 0.35 to 0.53, and is below the threshold of 1/2 of the standard deviation for clinical significance. Thus any meaningful differences between arms will be captured with the proposed sample size. If the differences between trial arms correspond to the adjusted effect size smaller than 0.44, the effect size will be estimated in this study and used to power future clinical trial studies.

**10. Minimal Risk Research.** Complete the following question if you selected an expedited category in Question 8A.

- A.** Briefly describe the background for conducting the research. (1-2 sentences)

- B.** Sample Size.

- i. Provide an estimated sample size for the lifetime of the study at this investigator's sites.

- ii. Describe the basis for that estimate.

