### B. Describe how subjects will be identified and recruited, including who will perform the recruitment.

This study will enroll 100 households where the mother is the principal caregiver and food preparer for one or more children from 1 to 4 yrs of age. If multiple biological children for a study mother are in that age range, they will all be enrolled and assigned as a household to the same caregiver training trial arm (either MISC/WTM or WTM only). However, the mother cannot be diagnosed with konzo following a full neurological exam at study enrollment, so that she is able to fully implement MISC and/or WTM training. Randomization occurs by geographic location (i.e. village) rather than individually to minimize the likelihood of contamination and diffusion effects within a community. Our MISC biweekly year-long caregiver training with rural Ugandan HIV mothers using MISC training resulted in a pre- to post-year retention rate of over 90% in our dyads, and we anticipate at least that retention rate given the fact that our mothers and children are not affected by HIV and those health and motivational issues.

We will randomly select our eligible households from a health zone census already established by the PRONANUT for Kahemba district in preparation for the R01 peer- versus professional-led non-inferiority clinical trial for teaching small groups of mothers the use of WTM to detoxify their cassava flour before eating. The present study will stratify its sample selection so that half of the participating households will be from peer- and half will be from professional-led health zones. Ho Also, the mothers of the study children are responsible day-to-day for cassava flour preparation. Mother and child have no prior history of severe medical condition or brain infection, accident, or injury which may preclude the ability to learn WTM and/or MISC and benefit from it in terms of functionality (maternal) or neurodevelopmental (child) outcomes. Once enrolled, they will be

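### The protocol gives two units of randomisation, household and village, and its stated detectable effects allow for no clustering by village

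*Combined protocol and SAP*

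**What the plan says.** **Unit of randomisation.** Section 12.A carries both versions in consecutive sentences: "Enrollment and randomization will occur at the village level", and then, after baseline in 100 households, "66 of them will be randomly selected to undergo individualized MISC+WTM training sessions by peers trained in the MISC+WTM curriculum". Section 1 has the household version: "Training 66 randomly selected moms from a cohort of 100 on MISC/WTM". Section 12.B has the village version, with contamination within a community as the reason: "Randomization occurs by geographic location (i.e. village) rather than individually". Section 2 (Procedures) puts the two into one sentence, in which dyads are randomised by cluster and a fixed 66 of 100 households receive MISC/WTM. Later in section 12.B the villages are said to be assigned to peer-led or specialist-led training. That matches the comparison of the parent R01 trial, not MISC/WTM against WTM only.

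**Detectable effect.** Section 9.B.iii starts "With n=66 in MISC+WTM arm and n=34 in WTM only arm" and adds that "we expect an over 90% retention rate for the full year". On that basis "the unadjusted effect size of 0.60 is detectable as statistically significant with power of 0.80 and 0.05 level of significance in two-tailed tests". It continues: "Assuming correlation of 0.4 between pairs of repeated measures seen in past testing of MISC, the adjusted detectable effect size is 0.44". It compares 0.44 with effects of 0.35 to 0.53 in earlier MISC work, notes that it lies below half a standard deviation, and concludes that no meaningful difference would be missed. The same section says that the sample size itself rests on timeline and resources.

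No section gives the number of villages, households per village, an ICC or a design effect. The only analysis features described are two follow-up measures and adjustment for baseline.

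**The concern.** The unit of randomisation decides who receives which training and which analysis is valid. If households are drawn from the pool of 100, MISC/WTM and WTM-only mothers can live in the same village, and the spillover that section 12.B sets out to prevent becomes possible. If whole villages are allocated, households in a village are likely to resemble each other, so 66 and 34 households carry less information than 66 and 34 independent ones. An analysis that ignored this would understate standard errors and inflate the type I error. Section 9.B.iii intends the effect estimate to power later trials, so an error in its precision would carry forward.

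**Working it through.** **1. Reproduce the stated figures.** Inputs from section 9.B.iii: 66 and 34 households, two-sided 0.05, power 0.80, correlation 0.4, two follow-up measures, baseline as covariate.

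- Unadjusted detectable effect = (1.960 + 0.842) × √(1/n₁ + 1/n₂).
- At 66/34: 2.802 × 0.2111 = 0.591, which rounds up to about 0.60.
- At exactly 90% retention (59.4/30.6): 2.802 × 0.2225 = 0.623. So 0.60 matches almost no attrition rather than 90% retention. This is a separate and smaller point, and nothing below depends on it.
- Adjustment factor = √((1 + 0.4)/2 − 0.4²) = √0.54 = 0.735, and 0.60 × 0.735 = 0.441. This reproduces 0.44.

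These formulas treat every household as independent; no village term is needed to reach 0.60 or 0.44.

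**2. Add village clustering.** Design effect DE = 1 + (m − 1) × ICC, where m is the number of retained households per village. The detectable effect is multiplied by √DE. Power at the stated effect becomes Φ(2.802/√DE − 1.960). With 90 retained households, 20, 10 or 5 equal villages give m = 4.5, 9 or 18. Village counts, equal sizes and ICCs are assumptions, and the same ICC is applied to the adjusted outcome.

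Example, 10 villages and ICC 0.05: DE = 1 + 8 × 0.05 = 1.40 and √DE = 1.183. Then 0.60 × 1.183 = 0.71, 0.44 × 1.183 = 0.52, and power is Φ(0.408) = 66%.

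| Villages | ICC | DE | 0.60 becomes | 0.44 becomes | 80% power becomes |
|---|---|---|---|---|---|
| 20 | 0.01 | 1.035 | 0.61 | 0.45 | 79% |
| 20 | 0.05 | 1.175 | 0.65 | 0.48 | 73% |
| 20 | 0.10 | 1.35 | 0.70 | 0.51 | 67% |
| 10 | 0.01 | 1.08 | 0.62 | 0.46 | 77% |
| 10 | 0.05 | 1.40 | 0.71 | 0.52 | 66% |
| 10 | 0.10 | 1.80 | 0.80 | 0.59 | 55% |
| 5 | 0.01 | 1.17 | 0.65 | 0.48 | 74% |
| 5 | 0.05 | 1.85 | 0.82 | 0.60 | 54% |
| 5 | 0.10 | 2.70 | 0.99 | 0.72 | 40% |

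The table takes the stated 0.60 and 0.44 as correct at 80% power, so it isolates clustering. It includes no loss for the few degrees of freedom between villages (18, 8 and 3 if counted as villages minus 2).

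**3. Where the half-SD argument fails.** With 10 villages, 0.44 × √DE passes 0.50 when DE exceeds (0.50/0.44)² = 1.291, that is, when the ICC exceeds 0.291/8 = 0.036.

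**4. Does the 66/34 split matter?** Before attrition and clustering, by the noncentral t with the same 0.735 factor, the adjusted effect is 0.424 at 60/40, 0.439 at 66/34 and 0.454 at 70/30. A shift of about 0.015 either way is small beside the clustering effect.

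**The case against.** The strongest reply is that the intended design can be inferred. Section 2 joins cluster randomisation to the household count, section 12.B twice prefers villages to individuals and says why, and section 12.A opens at village level. The household sentences may be shorthand for a target. The trial biostatistician, not field staff, generates the sequence, so a misreading in the field is not certain. The study is also exploratory, with a sample size set by resources.

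Much of this stands. Village allocation is the likelier intention, and contamination is a risk under one wording, not a predicted event. But the reply does not supply a village count or quotas, and it makes the detectable-effect problem more relevant, because the likelier design is the one that section 9.B.iii does not cover.

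A reader might infer three stronger things that the documents do not support:

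- That 66/34 cannot be reached by randomising villages. With equal village sizes it would need 1 or 2 households per village, but no section requires equal sizes. Planned quotas such as 33 + 33 against 34 give it exactly.
- That the planned analysis uses the wrong unit. No analysis unit is stated; what can be said is that no village-level analysis is described.
- That the sample size was miscalculated. It was not derived from power. The exposed statements are the detectable effects and the claim that nothing meaningful would be missed.

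**Conclusion.** The concern holds for the contradiction and for the detectable-effect statement. Sections 1 and 12.A, as worded, describe a different design from the preceding sentence of 12.A and from 12.B. Under village allocation, 0.60 and 0.44 are too favourable. At ICC 0.01 the adjusted figure moves only to 0.45 to 0.48 across 20 to 5 villages. At ICC 0.05 it is 0.48 to 0.60, and the upper end lies beyond the whole 0.35 to 0.53 range that the protocol cites. The size therefore depends on two quantities that the documents do not give, the village count and the ICC, and should be read as a range. An inexact split is a minor matter. Under household allocation no village inflation is needed, but the protocol's own safeguard against contamination is lost.

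**What to change.** - In sections 1, 2, 12.A and 12.B, state one unit: villages allocated to MISC/WTM or WTM only. Remove or correct the peer-led versus specialist-led description of the assignment.
- Give the number of villages per arm and the household quota per village, compatible with the half-and-half selection from peer-led and professional-led zones in section 12.B. Call 66/34 a target unless the quotas deliver it.
- In section 9.B.iii, restate both detectable effects with a design effect over a range of ICCs. Remove or qualify the claim that any meaningful difference will be captured.
- Specify an analysis with village as the cluster and a correction for a small number of clusters.
- Establish whether allocation has happened: section 2 speaks of the sequence as already generated, section 12.B as still to be generated. If it exists, document the unit actually used and match the analysis and the detectable effect to it.

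The cost is protocol wording and one recalculation, with a less favourable detectable effect and slightly wider intervals. The sample size can stay as it is, since it rests on resources.

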### B. Describe how subjects will be identified and recruited, including who will perform the recruitment.

This study will enroll 100 households where the mother is the principal caregiver and food preparer for one or more children from 1 to 4 yrs of age. If multiple biological children for a study mother are in that age range, they will all be enrolled and assigned as a household to the same caregiver training trial arm (either MISC/WTM or WTM only). However, the mother cannot be diagnosed with konzo following a full neurological exam at study enrollment, so that she is able to fully implement MISC and/or WTM training. Randomization occurs by geographic location (i.e. village) rather than individually to minimize the likelihood of contamination and diffusion effects within a community. Our MISC biweekly year-long caregiver training with rural Ugandan HIV mothers using MISC training resulted in a pre- to post-year retention rate of over 90% in our dyads, and we anticipate at least that retention rate given the fact that our mothers and children are not affected by HIV and those health and motivational issues.

We will randomly select our eligible households from a health zone census already established by the PRONANUT for Kahemba district in preparation for the R01 peer- versus professional-led non-inferiority clinical trial for teaching small groups of mothers the use of WTM to detoxify their cassava flour before eating. The present study will stratify its sample selection so that half of the participating households will be from peer- and half will be from professional-led health zones. Ho Also, the mothers of the study children are responsible day-to-day for cassava flour preparation. Mother and child have no prior history of severe medical condition or brain infection, accident, or injury which may preclude the ability to learn WTM and/or MISC and benefit from it in terms of functionality (maternal) or neurodevelopmental (child) outcomes. Once enrolled, they will be

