## 2. Procedures.

Describe the research procedures that involve obtaining information or biospecimens about a living person through interaction or intervention and/or by obtaining their identifiable private information or identifiable biospecimens. If subjects will participate in or undergo an intervention, fully describe the intervention. If the procedures are longer than 1 page, provide a summary and include the full procedures as an attachment.

Caregiver/child dyads will be randomized (by cluster) whereby 66 of the 100 households will be selected to randomly receive MISC/WTM caregiver training to enhance caregiver mental health and functionality and early childhood development. The remaining 34 households will receive WTM only (considered the recommended standard of care for the prevention of konzo disease in at risk communities). This is in order to see if adding MISC to caregiver training enhances adherence to WTM for flour detoxification, corresponding child neurodevelopmental and caregiver functionality mental health outcomes – as compared to WTM alone for similar households. To maintain concealment of MISC training allocation, the randomization sequence was generated by the trial biostatistician located in the USA, who also serves as our clinical methodologist and biostatistician for the R01 WTM konzo prevention non-inferiority clinical trial.

The WTM intervention. The intervention will implement the WTM cassava processing technique in participating households. Twenty women with leadership and communication skills have already been trained and are implementing WTM in the R01 trial and will do the training for our WTM-only households in this R21 study. These are mothers who master the WTM technique and have been certified as trainers to train and support other small groups of other mothers. They have to be able to bring the cassava cyanogenic content to the lowest achievable level, which must be < 10 ppm as per the WHO recommendations.

The wetting method to remove cyanogens from cassava flour involves adding dry flour to a bowl and marking the level on the inside of the bowl. Water is then added with mixing, the volume of

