### **3. Subject Population.**

#### **A. Describe the subject population.**

We will study 100 non-konzo mother/child dyads, and all household children 12 to 48 months of age. 34 mother/child pairs will receive 12-months of biweekly home-based personalized training sessions with wetting method (WTM) training only to detoxify cassava flour in the prevention of konzo, and 66 dyads will receive 12 months of MISC caregiver training to improve early childhood development (ECD) combined with WTM. These families represent a homogenous population of Congolese people living in the Kahemba district of the Bandundu Province, Democratic Republic of Congo (DRC) in southwestern Bandundu province. People in this rural district depend heavily on daily cassava root and leaves for food and cash income. A typical population of 100,000 cultivates about 5000 hectares of cassava per year. Traditional varieties of cassava, which are subject to the cassava mosaic virus, yield around 6 tons/hectare per year. Crop losses in the 1990s ranged from 5% to 95%, thereby resulting in severe food insecurity. Cassava dependency resulted in up to 5% of individuals in affected villages developing walking difficulties typical of konzo. A substantially larger percentage (estimated up to 10%) has neurological signs and symptoms of an earlier stage of konzo in which ambulatory difficulty is not overt. Our recent findings suggest that deficits in cognition may also be part of neurological picture. Therefore, this is an at-risk population.

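### All eligible siblings are enrolled in the same arm, but the only analysis described has no household or village term, so child-outcome standard errors would be too small if every child is analysed that way

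*Combined protocol and SAP*

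**What the plan says.** Section 3.A sets the sample: "We will study 100 non-konzo mother/child dyads, and all household children 12 to 48 months of age". Section 12.B makes the sibling rule explicit, with siblings following their mother into one arm: "If multiple biological children for a study mother are in that age range, they will all be enrolled and assigned as a household". Section 2 gives the child test battery to the children at baseline, six months and one year. No section names an index child.

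Randomization is described as being by village in Sections 12.A and 12.B. Section 12.A also says that 66 of the 100 households are drawn at random after baseline, and Section 2 has: "66 of the 100 households will be selected to randomly receive MISC/WTM caregiver training".

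The only account of an analysis is the sample-size justification in Section 9.B.iii. Its units are: "With n=66 in MISC+WTM arm and n=34 in WTM only arm". The arm effect is to be estimated "from two repeated measures at 6 and 12 months with the planned covariance adjustment for baseline", and one correlation is supplied: "Assuming correlation of 0.4 between pairs of repeated measures seen in past testing of MISC, the adjusted detectable effect size is 0.44". Nothing there or elsewhere mentions household, sibling or village correlation.

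Aim 3 (Section 1) explores whether caregiver wellbeing and functioning mediate the child outcomes. It gives no model, no unit of analysis and no rule for a mother with more than one enrolled child.

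**The concern.** Siblings share a mother, a home, the household's flour and a trainer, so their scores will be correlated. An analysis that places every child in the data and allows only for correlation between visits treats two siblings as two independent children. P-values would then be too small and intervals too narrow for the child outcomes: Mullen, Fagan, vigilance test, COAT and child urinary thiocyanate. Section 9.B.iii intends the estimated effects to inform the power of later trials, so overstated precision would carry forward.

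The silence also leaves a choice open until data are in hand: all children, one child per mother, or a household mean. In Aim 3, the mediator has one value per mother while the outcome may have two or more values per household, so the unit matters there as well.

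**Working it through.** **1. Reproduce the plan's figures.** Inputs from Section 9.B.iii: 66 and 34 units, two-sided 0.05, power 0.80, correlation 0.4, and "we expect an over 90% retention rate for the full year".

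- Unadjusted detectable effect = (1.960 + 0.842) × √(1/n₁ + 1/n₂). With 66 and 34 this is 0.591. With 59.4 and 30.6 (exactly 90% retained) it is 0.623. The stated 0.60 corresponds to about 64 and 33.
- Adjustment for one baseline and the mean of two follow-ups: √((1 + 0.4)/2 − 0.4²) = √0.54 = 0.735. Then 0.60 × 0.735 = 0.441, the stated 0.44. From 0.623 it is 0.458.

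The stated figures therefore reproduce with no clustering term of any kind, and with households as the unit.

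**2. Effect of ignoring siblings.** Assumptions, because the documents give no values: a share q of households has two eligible children and the rest have one; the sibling correlation is ρ.

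- Mean children per household: m = 1 + q.
- Household size weighted by child: w = (1 + 3q)/(1 + q).
- Design effect: D = 1 + (w − 1)ρ.
- Correct SE / naive SE = √D.
- Actual error of a nominal 5% test = 2 × [1 − Φ(1.96/√D)].

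| q | ρ | w | D | √D | Actual error |
|---|---|---|---|---|---|
| 20% | 0.2 | 1.333 | 1.067 | 1.03 | 5.8% |
| 40% | 0.4 | 1.571 | 1.229 | 1.11 | 7.7% |
| 60% | 0.6 | 1.750 | 1.450 | 1.20 | 10.4% |

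A simulation of the naive child-level t-test (59 and 31 households, 8,000 runs per cell) rejected 6.1%, 7.8% and 10.8% of the time in these three rows. Village correlation is set to zero here.

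**3. Effect on power.** A correct child-level analysis at 90% retention has detectable adjusted effect 0.458 × √(D/m).

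- 20%, 0.2: 0.458 × √(1.067/1.2) = 0.432.
- 40%, 0.4: 0.458 × √(1.229/1.4) = 0.429.
- 60%, 0.6: 0.458 × √(1.450/1.6) = 0.436.

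All are below the 0.458 from one child per household. In the middle case, 126 children in 90 households are worth 126/1.229, or about 102 independent children. Siblings add information; they do not erode the stated power.

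**4. Would a village term be enough?** This was simulated with an assumed 15 villages of 6 households, village correlation 0 or 0.05, and 4,000 runs per cell.

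- Arm effect, t-test on village means: 4.5% to 5.7% rejection in all three rows. Siblings lie inside the randomized village, so inference at that level absorbs their correlation.
- Mother-to-child path, village fixed effects, child rows otherwise independent: 5.7% to 6.4%, 7.8% to 8.3% and 10.9% to 11.1% in the three rows. A mother-level predictor is identical for siblings, so the design effect is again 1 + (w − 1)ρ, and the village term leaves it in place.

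**5. A maternal outcome copied onto each child's row.** Here ρ = 1, so D = w and √D = 1.15, 1.25 and 1.32. The actual error is 9.0%, 11.8% and 13.8%. This applies only if the data are laid out in that way.

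**The case against.** The strongest reply is that randomization is by village, so a proper village-level analysis already protects the arm comparison and a household term is a refinement. For the arm effect this stands, as step 4 shows. It would be wrong to infer that sibling correlation always survives a village term. The reply has three limits: no village-level analysis is planned; the mother-to-child path is not protected; and if the household draw in Section 12.A is taken literally, the household is the allocated unit and village-level inference no longer matches the allocation.

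A reader might also infer that enrolling siblings makes the sample size too optimistic. It does not: 66 and 34 count households, and "the unadjusted effect size of 0.60 is detectable as statistically significant with power of 0.80 and 0.05 level of significance in two-tailed tests" reproduces on that basis.

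A reader might infer that the plan specifies a model treating siblings as independent, or that mothers of two children count twice in Aim 3. Neither is written. Section 9.B.iii is a power paragraph, not a full model, and Aim 3 gives no unit. Both are risks left open by silence.

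Finally, the size rests on assumed inputs, and the correlation that matters is the one remaining after baseline adjustment, which may lie toward the low end. The study is also exploratory. These points limit the size of the problem; they do not supply the missing rule.

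**Conclusion.** The concern holds as a gap in the analysis plan. All eligible siblings enter the study in the same arm, and the only analysis described allows for correlation between visits alone. If every child is analysed that way, the correct standard errors for child outcomes are about 3% to 20% larger than those reported, and the actual error is about 6% to 11% at a nominal 5%. That range assumes 20% to 60% of households with two eligible children, none with more, a sibling correlation of 0.2 to 0.6 and no village effect.

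The missing village term is a larger gap. A village correlation of 0.02 to 0.10 with 5 to 10 households per village (also assumed) would raise the 0.458 to between 0.48 and 0.63. A household term alone would not repair that, so the two levels should be specified together. The remedy should be adopted, but the matter does not threaten the feasibility of the trial.

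**What to change.** State the following in the analysis plan before outcome data are examined:

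- **Child outcomes:** the baseline-adjusted repeated-measures model, with visits within child, child within household and household within village.
- **Flour cyanogen, maternal urinary thiocyanate, Hopkins checklist and caregiver functioning:** one record per household at each visit.
- **Aim 3:** relate the mother's mediator to the household mean child score, or use the same multilevel model. Name the unit.
- **Sensitivity analysis:** one index child per household, drawn at random before allocation, or by a documented random draw made without reference to outcomes if allocation has already taken place.
- **Reporting:** the number of enrolled children per household by arm and the estimated household and village correlations, which a later trial will need.

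The cost is analysis wording only. No extra data or participants are needed. Intervals will be slightly wider than from a naive child-level analysis, and power with respect to siblings is no lower than with one child per household.
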